**Study Title: Modulating brain activity to improve goal-directed physical activity in older adults**

**NCIT number: NCT04278560**

**Date of the document: 10/27/2023**

### **Statistical Methods**

Overall approach: Exploratory analyses will be used to assess outcomes distributions, and any necessary transformations (e.g., to combat significant skew) will be performed prior to estimation of mean treatment effects. Said estimation will use mixed effects linear regression of post-intervention within three days after the last brain stimulation session and again within three days after the last behavior session, with random intercepts and slopes to account for serial correlation in repeated measurements on individuals. Models will control for baseline outcomes in analysis of covariance.

Two-way repeated-measures ANOVA will be used to examine the effect of intervention on primary and secondary functional outcomes. The effect of the 10-session tDCS intervention on the primary functional outcome (daily step count) will be analyzed with a two-way repeated-measures ANOVA. The dependent variable will be *the change in average daily step count from the two-week baseline to each two-week study period of the behavioral intervention*. Model effects included group (tDCS, sham), time (two-week period), and their interaction. The effect of intervention on secondary functional outcomes, which will be collected at baseline, after the two-week brain stimulation intervention, and after the behavioral intervention. Dependent variables will be *the changes in each functional outcome from baseline to each follow-up visit*. The model's effects included group (tDCS, sham), time (post-stim, final) and their interaction.

The feasibility outcomes are the completion rates for the brain stimulation sessions and the behavior sessions, respectively. We will use independent t-tests to examine the differences between two study arms.

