Assessment of feasibility endpoints will be based on sample computations, including the screened to enrolled ratio, retention rate, assurance of blinding, and safety assessment (see above). Adverse events (AE) will be organized according to the MedDRA classification system and reported in each DSMB communication both by MedDRA System Organ Class (SOC) and overall. Both the number of individuals with one or more of AEs within each SOC, as well as the total count of all AEs within each SOC, will be reported. These will be accompanied by point and 95% confidence interval estimates of the proportion of individuals who would experience AEs and the total count of AEs per person-time within each SOC, respectively. The latter computation will acknowledge clustering at the level of the participant by using generalized estimating equations (GEE) in estimation with robust variance estimates used for computing confidence intervals.

We will use variance decomposition to generate estimates of within and between-individual variation in functional outcomes that would potentially be used in a subsequent trial (see above), along with confidence interval estimates for said variance measures, in order to assist in planning of the subsequent study. We will also conduct an exploratory analysis of the mean change in these endpoints using mixed-effects linear regression of all time points, with a random effect included at the participant level in acknowledgement of serial correlation of repeated measures. Dependent variables will be the change in outcomes related to average daily activity from baseline to the six-week post-tDCS follow-up period, as well as the change in laboratory-based functional outcomes from baseline to each planned follow-up visit.

Feasibility outcomes:

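### The SAP's random intercepts and slopes are not identified from two post-intervention assessments, so its mixed model cannot separate within- from between-participant variance

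*SAP*

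**What the plan says.** **SAP, Statistical Methods, overall approach.** Mean treatment effects are to be estimated by mixed-effects linear regression of measurements taken "post-intervention within three days after the last brain stimulation session and again within three days after the last behavior session". The same sentence then gives the random part of this model, which is to be fitted "with random intercepts and slopes to account for serial correlation in repeated measurements on individuals". On baseline it says: "Models will control for baseline outcomes in analysis of covariance". Baseline is thus a covariate, not a response. No covariance structure is given for the random effects.

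**SAP, second paragraph.** Secondary outcomes also go to a two-way repeated-measures ANOVA with two time levels: "The model's effects included group (tDCS, sham), time (post-stim, final) and their interaction". Step count has its own ANOVA, on "the change in average daily step count from the two-week baseline to each two-week study period of the behavioral intervention". The number of two-week periods is not stated.

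**Protocol, Data Analysis.** The plan is: "We will use variance decomposition to generate estimates of within and between-individual variation in functional outcomes", with confidence intervals, to help plan the next study. As a further item it describes an exploratory mixed model of all time points, "with a random effect included at the participant level in acknowledgement of serial correlation of repeated measures". It names no slope there and does not say which model supplies the variance estimates. The SAP does not mention those estimates.

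**The concern.** A random slope needs enough occasions per person to tell a person's own trend from occasion-to-occasion noise. With two responses per person, a personal line passes through both points exactly, and nothing is left to estimate the noise. An analyst following the SAP literally will meet a failed or degenerate fit, or will report variance components that reflect the software's starting values. The analyst must then choose a simpler structure after seeing the data.

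This matters more in a pilot than it would elsewhere. The split between within- and between-individual variation is one of the protocol's stated products, and the SAP, which is the later document, names no other source for it.

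**Working it through.** The documents give no figure for this point, so there is none to reproduce. The numerical examples below use assumed variances.

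**1. Inputs.** Two response occasions, baseline as covariate, random intercept and slope (SAP, Statistical Methods). 26 evaluable participants (Protocol, Data Analysis).

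**2. Count.** Two occasions give 2 variances + 1 covariance = 3 moments. The model has intercept variance s00, slope variance s11, their covariance s01 and residual variance s2, which is 4 parameters. The 3x4 Jacobian of the moments in these parameters has rank 3. Equivalently, 26 participants give 26 x 2 = 52 observations and 26 x 2 = 52 random effects.

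**3. Example.** Code time 0 and 1:
- V1 = s00 + s2
- C = s00 + s01
- V2 = s00 + 2 s01 + s11 + s2

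Set V1 = V2 = 1 and C = 0.6. Then s00 = 1 - s2, s01 = s2 - 0.4 and s11 = 0.8 - 2 s2.

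| s2 | s00 | s01 | s11 |
|---|---|---|---|
| 0.4 | 0.6 | 0 | 0 |
| 0.2 | 0.8 | -0.2 | 0.4 |
| 0 | 1.0 | -0.4 | 0.8 |

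All three rows are valid and give the same covariance matrix. The residual share can be anything from 0 to 40% of the total variance.

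**4. Likelihood check.** Data were simulated for 26 participants with visits at weeks 0 and 6 (intercept variance 0.5, slope variance 0.01, residual 0.5, no intercept-slope covariance).
- *Nominal visit times:* -2 REML is 50.6702 at every residual variance tried from 0.01 to 0.5.
- *Actual days spread over 0 to 3 days, as the SAP windows allow:* it moves from 55.69 at 0.01 to 56.32 at 0.5, a change of 0.63, and is lowest at 0.01 although the true value is 0.5. The windows do not rescue the model.
- *Baseline added as a third response:* there is a clear minimum near 0.4 (66.17, against 74.19 at 0.2 and 69.55 at 0.7).

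**5. Zero intercept-slope covariance.** Three parameters now face three moments. For times t1 and t2, s11 = (V2 - V1)/(t2² - t1²), s00 = C - t1 t2 s11 and s2 = V1 - s00 - t1² s11. Take V1 = 1, C = 0.5, V2 = 1.36:
- Weeks coded 0 and 6: s11 = 0.36/36 = 0.01, s00 = 0.5, s2 = 0.5.
- Weeks coded 2 and 8: s11 = 0.36/60 = 0.006, s00 = 0.5 - 16 x 0.006 = 0.404, s2 = 1 - 0.404 - 0.024 = 0.572.

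The data are the same, but the within-person variance differs. If time is centred (t1 = -t2), V1 and V2 have the same expression and even this version is not identified.

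**6. What is identified.**
- Random intercept only, two visits: 3 moments, 2 parameters, rank 2. In simulation with n = 26 and true residual 0.5, the mean estimate was 0.497 (central 95% range 0.26 to 0.81).
- Intercept and slope with baseline as a response: 6 moments, 4 parameters, rank 4. With four occasions: 10 moments, rank 4.

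**7. Effect of adjusting for baseline.** Assume compound symmetry, total variance 1 and intraclass correlation 0.6. The between-person variance is 0.60. Given baseline, the covariance of two follow-ups is 0.6 - 0.6² = 0.24 and the variance is 1 - 0.6² = 0.64. The within-person variance stays at 0.40, so its share rises from 40% to 0.40/0.64 = 62.5%.

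**The case against.** The best defence is that little of the trial's inference depends on this. Fixed effects depend on the marginal 2x2 covariance, which the data do determine: every row of the table in step 3 gives the same matrix, hence the same treatment estimates and standard errors. The SAP also assigns the functional outcomes to repeated-measures ANOVA, which has no random slope. All of this stands.

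A second defence is that the SAP leaves the random-effects structure open, so an analyst could take intercept and slope as independent. That is possible, but the SAP states no such constraint, and step 5 shows that the result would depend on time coding.

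Two stronger readings are tempting, and the documents support neither.
- *The variance estimates promised for the next trial cannot be obtained.* The protocol lists variance decomposition as its own task and describes a model of all time points with a single participant effect. The SAP uses the random-slope model only for mean treatment effects. The promised estimates remain available by another route.
- *The visit schedule cannot support slopes.* The SAP collects secondary outcomes at baseline, after stimulation and after the behavioural intervention, and the protocol's Visit 14 text adds an assessment two weeks after stimulation. Three occasions are enough. The limit arises because baseline enters as a covariate. Step counts over three or more two-week periods, or trial-level dual-task data, could also supply more occasions, but the SAP does not put them in this model.

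**Conclusion.** The point holds for the model as written. With a free intercept-slope covariance and a residual, four variance parameters face three moments, so the within/between split is undetermined. In the example, the within share lies anywhere from 0 to 40%. That range depends on the assumed variances; the lack of identification does not.

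The consequence is limited. Treatment effects and the total covariance survive, and the protocol's variance decomposition is not ruled out. What is lost is any usable split from this SAP model, together with a pre-specified covariance structure. The SAP should be corrected on this point, but it does not threaten the treatment comparison.

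**What to change.** - **Treatment-effect model.** For outcomes with two post-baseline visits, delete the words 'and slopes'. Fit group, visit, group-by-visit and baseline with either a participant random intercept or an unstructured 2x2 residual covariance. State in advance which one. The random intercept assumes equal variance at the two visits; the unstructured form does not.
- **Variances for the next trial.** Add a sentence to the SAP naming their source: a separate random-intercept model with baseline and all follow-up visits as responses, in line with the protocol's model of all time points, reported with confidence intervals. Do not take them from the baseline-adjusted model. Its intercept variance is conditional on baseline and would understate between-person variation (0.24 instead of 0.60 in step 7).

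The cost is two words deleted and a few sentences added. Data collection and conduct do not change.

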Final follow-up assessments, as described above in Visit 2, will be completed after 6 weeks of the tDCS intervention.

At the end of visit 18, we will provide the opportunity for participants to continue tracking their FitBit information for up to additional 3 months. If the participant agrees, we will keep the tracking option available for the study team to track the retention of the intervention. The study team will terminate this tracking service by the end of the retention phase.

Materials for recruitment and study conduct

StimFit_Recruitment_Flier_20200108_clean.pptx

StimFit_Recruitment_Flier_notabs_20200108_clean.pptx

StimFit_Recruitment_letter_20200205_tracked IRB edits_clean.doc

Assessment of Protocol Understanding Form.docx

International Physical activity Questionnaire IPAQ short procedure Q by Q and questions.docx

MOCA.pdf

Stim-Fit_Phone_Screen_2020205_clean.docx

Stim-Fit_tDCS_Eligibility_Questionnaire.docx

The PAR Q.docx

gradCPT Instructions_FrailAdults.docx

N-Back_Instruction.docx

TRAILS_V1.pdf

TRAILS_V2.pdf

Trails_v3_corrected.docx
Digit Span.pdf
Blood Pressure Form_42219.docx
DT Balance Assessment 42219.docx
DT familiarization and sitting assessment 42219.docx
DT gait assessment 42219_AlipgEdit.docx
GDS15.pdf
Height and Weight Form 42219.docx
Medical History Questionnaire_1 71318.docx
Medication Review Form_1 42219.docx
Sociodemographic Form 42219.docx
TUG form 42219.doc
BARSE.pdf
ESES worksheet_exercise_self-efficacy_scale_eses_0.docx
SEW_DUR.pdf
SRQ-Exercise_short.pdf
WHAS Pain Questions.docx
tDCS Blinding Efficacy.docx
tDCS Side Effects Questionnaire.docx
Cognitive Reserve Questionnaire.pdf

Data Analysis and Data Monitoring

Data Analysis

This study will enroll 32 participants. We have conservatively planned for approximately 20% attrition and have thus based our statistical plan on complete datasets of $n = 26$.

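### For daily step count, the SAP's repeated-measures ANOVA names no test term, lists no baseline covariate and has no rule for missing fortnights; one baseline-adjusted mixed model would settle all three

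*SAP*

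**What the plan says.** The SAP's Statistical Methods section describes two analyses of the functional outcomes.

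- The paragraph labelled Overall approach specifies "mixed effects linear regression of post-intervention within three days after the last brain stimulation session" and again after the behavioural sessions end. It adds: "Models will control for baseline outcomes in analysis of covariance".
- The next paragraph says "Two-way repeated-measures ANOVA will be used to examine the effect of intervention on primary and secondary functional outcomes" and assigns step count to that ANOVA by name. The outcome is "the change in average daily step count from the two-week baseline to each two-week study period of the behavioral intervention". The effects are given in one sentence: "Model effects included group (tDCS, sham), time (two-week period), and their interaction".

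The SAP does not rank the two analyses, name a test term or mention missing data.

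The protocol adds four relevant statements.

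- Under Data Analysis, the investigators "have thus based our statistical plan on complete datasets" of 26 out of 32 enrolled.
- Under Functional outcomes, attrition and missingness together are put at about 20%.
- Under Participant Withdrawal, data collected before withdrawal are kept.
- Data Analysis also describes an exploratory mixed model in which the activity outcome is change to the six weeks after tDCS.

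**The concern.** Three choices that affect the step-count result are left to the analyst.

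1. **Term.** The outcome is already a change from baseline. The group term therefore tests an average benefit, and the interaction tests whether the benefit varies over time. These are different claims, and the SAP lists both terms without choosing.
2. **Baseline.** The covariate appears in the mixed-model paragraph but not among the ANOVA effects. Whether it carries over is open.
3. **Missing fortnights.** A classical repeated-measures ANOVA drops anyone with a missing period. The protocol expects losses and keeps the partial data, so observed fortnights would go unused.

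The protocol says the pilot's data will help plan the next trial. An estimate whose test term and analysis set can be settled after the data are seen is a weak basis for that.

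**Working it through.** **The plan's own figure.** No figure in the plan bears on these choices. The protocol's power statement concerns a within-participant difference, which is neither ANOVA term. Its conversion to steps reproduces (0.41 × 150 = 61.5; 0.36 × 150 = 54). Its power does not: a two-sided paired t-test on 26 gives 52% at 0.41 and 42% at 0.36. That is a separate matter and does not identify the test term.

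**Inputs from the documents.** 16 per arm randomised; 26 complete, taken as 13 per arm; alpha 0.05; eight weeks of step monitoring, so K = 4 fortnights.

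**Assumptions not in the documents.** Two-sided tests, normal data, SD 1 in each period. The pairs of baseline-to-period correlation ρ and period-to-period correlation τ are (0.5, 0.7), (0.6, 0.8) and (0.7, 0.8). Results separated by slashes follow that order.

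**1. Term.** If either of two independent 5% tests counts, type I error is 1 − 0.95² = 9.75%. Simulating the ANOVA with 13 per arm and sphericity true gives 9.8–9.9%. For a constant 0.8 SD benefit, power is 60/68/83% for the group term and about 5% for the interaction. The choice can also go the other way. For a benefit growing from 0 to 1.5 SD, with all correlations equal at 0.5 to 0.85, power is 64–99% for group and 93–100% for interaction.

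**2. Baseline, only if the ANOVA omits it.** Per-participant variance of the K-fortnight mean: V = (1 + (K − 1)τ)/K. Change score: V + 1 − 2ρ. ANCOVA: V − ρ².

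| ρ, τ | V | Change | ANCOVA | Ratio | 80% power becomes |
|---|---|---|---|---|---|
| 0.5, 0.7 | 0.775 | 0.775 | 0.525 | 0.68 | 91% |
| 0.6, 0.8 | 0.850 | 0.650 | 0.490 | 0.75 | 88% |
| 0.7, 0.8 | 0.850 | 0.450 | 0.360 | 0.80 | 86% |

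The last column uses the noncentral t and multiplies the ANCOVA variance by 1 + 1/22 for chance baseline imbalance. With K = 3 the ratios are 0.69/0.76/0.81. Under randomisation both estimators are unbiased.

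**3. Missing fortnights, precision.** If fortnights go missing independently, 26 of 32 complete corresponds to 1 − (26/32)^(1/4) = 5.06% missing per fortnight. Observed fortnights are then 32 × 4 × 0.949 = 121.5. The 26 completers hold 104, which leaves about 17.5 with the other six, or 2.92 each. A complete-case ANOVA discards those.

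With baseline adjusted in both analyses, generalised least squares on 13 complete plus 3 incomplete participants per arm gives these variances relative to complete-case:

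- one leaving after each of fortnights 1, 2 and 3: 0.83–0.84
- all three leaving after fortnight 1: 0.86–0.87
- each missing one fortnight: 0.82

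The floor is 13/16 = 0.81. At these values 80% power becomes 86–88%. The calculation assumes known covariance and at least one post-baseline fortnight per non-completer, so it is slightly optimistic.

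**4. Missing fortnights, bias.** There is no true effect, and 3 of 16 per arm leave after fortnight 1.

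- Random loss in both arms: no bias.
- The three lowest on fortnight-1 change leave in both arms: no bias.
- The three lowest leave in one arm, with random loss in the other: the complete-case difference is off by 0.15–0.18 SD with baseline adjusted (type I error 10–11%). With moderate dependence instead, it is off by 0.09–0.10 SD (6–7%).
- In these one-arm scenarios a random-intercept model with baseline, using all fortnights, stays within 0.01 SD (type I 5–6%). The data were simulated with equal period correlations, which is that model's best case.

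**The case against.** **The group term is the natural test.** The outcome is a change score and the stated purpose is the effect of the tDCS course. This is the sensible reading, and the fix adopts it. But the SAP lists the interaction on equal footing and never says so.

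**Overall approach may govern everything below it.** If it does, baseline is already adjusted and the precision loss in step 2 disappears. That reading is open, but the ANOVA's effect list omits baseline and does not refer back. A reader might infer that the SAP definitely runs an unadjusted ANOVA, or that the result would be biased. The text does not establish the first, and randomisation rules out the second.

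**Missing fortnights may be few.** Staff monitor uploads and synchronise devices, and a fortnightly average survives scattered missing days. The SAP also does not say that it uses the classical listwise form. These points lower the likely loss but supply no rule. The complete-datasets wording in the protocol is a sizing assumption; it does not say how incomplete participants are analysed.

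**The bias can be overstated.** Comparing an unadjusted complete-case change score with a baseline-adjusted mixed model gives 0.18–0.24 SD in the extreme case. Part of that gap comes from baseline adjustment, and 0.15–0.18 SD is the like-for-like figure. It also needs outcome-driven loss in one arm only, which nothing in the documents suggests for a blinded trial.

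**The window is not undefined.** A reader might infer that it is. The SAP states one: each fortnight of the behavioural intervention. The protocol starts that intervention at the end of Visit 2, so by inference the stimulation fortnight is included. The protocol's six-week period after tDCS differs from this and needs reconciling.

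**Conclusion.** The point holds, as something that should be fixed in an exploratory pilot analysis. For step count the SAP names no test term, lists no baseline covariate in the ANOVA, and gives no rule for partly observed participants. About 10% type I error follows if either term can count, and the interaction has about 5% power for a constant benefit.

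The other sizes are conditional on the assumed correlations. If baseline is omitted, the cost is precision only, with an ANCOVA-to-change variance ratio of 0.68–0.80. Using all observed fortnights brings variance to about 0.82–0.87 of complete-case, slightly optimistically. Complete-case bias is a possibility under arm-specific, outcome-dependent drop-out, not an expected result. The documents do not support calling the planned estimate biased or the trial uninterpretable.

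**What to change.** Before unblinding, or as a dated amendment if unblinding has occurred, replace the step-count ANOVA with one primary analysis:

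- a likelihood-based mixed model of mean daily steps per fortnight, with baseline mean daily steps, group, period and group × period;
- a random participant intercept and small-sample degrees of freedom, with unstructured covariance as a sensitivity analysis, because a 4 × 4 matrix has 10 parameters and n is about 26 to 32;
- all randomised participants with any post-baseline fortnight, with a statement of what makes a fortnight count as observed;
- the group difference averaged over the SAP's stated fortnights as the primary contrast, with the interaction secondary.

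Reconcile the SAP's window with the protocol's six weeks after tDCS, and report the latter as secondary. Keep the change-score ANOVA only as a sensitivity analysis.

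The cost is SAP wording, one degree of freedom for baseline, and reliance on a missing-at-random assumption. No new data or participants are needed.
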